EpoR	Erythropoietin receptor
ESA	Erythropoiesis stimulating agent
FDA	Food and Drug Administration
FDG-PET	Fluorodeoxyglucose-PET
g/dL	Gram per deciliter
GBG	German Breast Group
GGT	Gamma-glutamyltransferase
GOG	Gynecologic Oncology Group
HIV	Human immunodeficiency virus
HR	Hazard ratio
HSA-free	Human serum albumin-free
ICF	Informed consent form
ICH GCP	International Conference on Harmonisation Tripartite Guideline on Good Clinical Practice
ID	Identification
IEC/IRB	Independent ethics committee/institutional review board
IP	Investigational product
IV	Intravenous
IVR/IWR System	Interactive Voice Response/Interactive Web Response System
PPD	
kg	Kilogram
LDH	Lactate dehydrogenase
LTFU	Long-term follow-up
MCH	Mean corpuscular hemoglobin
MCHC	Mean corpuscular hemoglobin concentration
MCV	Mean corpuscular volume
MDS	Myelodysplastic syndromes
mL	Milliliter
MRI	Magnetic resonance imaging

Abbreviation or Term	Definition/Explanation
NA	Not applicable
NE	Inevaluable
ng	Nanogram
NSCLC	Non-small cell lung cancer
ODAC	Oncologic Drug Advisory Committee
OR	Odds ratio
OS	Overall survival
PD	Progressive disease
PE	Physical examination or pulmonary embolism
PET	Positron emission tomography
PET-CT	Positron emission tomography-computer tomography
PFS	Progression-free survival
pg	Picogram
PICC	Peripherally-inserted central catheter
PIN	Personal identification number
PR	Partial response
Q3M	Once-every-3-months
Q3W	Once-every-3-weeks
Q9W	Once-every-9-weeks
QW	Once-weekly
RBC	Red blood cell
RECIST	Response evaluation criteria in solid tumors
rHuEPO	Recombinant human erythropoietin
SAE	Serious adverse events
SAER	Serious adverse event report
SCLC	Small cell lung cancer
Screening hemoglobin	Local laboratory hemoglobin; sample obtained within 7 days prior to randomization
Screening period	Starts when the subject signs and dates the informed consent form and ends when the subject is randomized or screen failed. Must not exceed 21 days.
SD	Stable disease
SUSAR	Suspected unexpected serious adverse reactions
TIA	Transient ischemic attack
TIBC	Total iron binding capacity
Tsat	Transferrin saturation

Abbreviation or Term	Definition/Explanation
Treatment period	Starts when the subject is randomized and ends at the next Q3W visit after disease progression has been determined (EOTP). Note that EOTP is based on disease progression, not IP dosing.
TVE	Thrombovascular event
μg	microgram
ULN	Upper limit of normal
US	Ultrasound
VTE	Venous thromboembolic event
WBC	White blood cell
Wk	Week

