6.2.2 Chemotherapy

Subjects should be expected to receive at least 2 additional cycles (at least 6 total weeks) of first line myelosuppressive cyclic chemotherapy (eg, standard doublet chemotherapy) after randomization. Subjects should not be expected to receive only maintenance chemotherapy. First line chemotherapy in combination with other targeted therapy (eg, biologics) that is considered acceptable standard for first line treatment of NSCLC is allowed. Chemotherapy regimens or combination therapies including chemotherapy will be dependent upon local standard and practices, however, chemotherapy regimens containing investigational agents (ie, not approved for any indication by the applicable regulatory authority) will not be allowed. If the first line chemotherapy regimen changes at any time during the study (eg, due to toxicity) or if optional myelosuppressive maintenance therapy is initiated, then the subject may receive IP as scheduled as long as the subject continues to receive myelosuppressive chemotherapy completely, IP will be discontinued within 3 weeks after the last dose of chemotherapy.

Chemotherapy regimen including date of administration will be recorded in the subject's CRF.

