7.1.8 Thrombovascular Events

All subjects will be monitored closely for clinical signs and symptoms of thrombovascular events (TVE) (arterial thromboembolic events [ATE]: stroke, transient ischemic attack

[TIA], acute coronary syndromes [ACS], other arterial thrombosis/embolism; venous thromboembolic events [VTE]: deep vein thrombosis [DVT], pulmonary embolism [PE], other venous thrombosis excluding superficial venous thrombosis). If any signs or symptoms are present, the subject will undergo specific laboratory and medical imaging studies to confirm VTEs. The medical imaging study or studies selected will depend on the anatomic site of the suspected VTE or organ of involvement (eg, Doppler ultrasound, venography, ventilation perfusion lung scan, angiography, MRI). If a VTE is confirmed, appropriate medical care according to standard local clinical practice should be initiated immediately.

TVEs will be documented in the CRF through the EOTP or 30 days after the last dose of IP, whichever occurs later.

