7.1.10 Adverse Events Reporting

Adverse events starting at randomization through 30 days after last dose of IP will be reported to Amgen. All serious adverse events (SAEs) occurring from the date the subject signs the ICF through 30 days after the last dose of IP will be reported to Amgen. All TVEs, and adverse events associated with RBC transfusions administered during the treatment period, will be reported through the EOTP or 30 days after the last dose of IP, whichever occurs later. Refer to Section 9 for more detail on adverse events reporting.

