9.1.2 Reporting Procedures for Adverse Events

All adverse events occurring after randomization through 30 days after last dose of IP as recorded in the subject's medical record, will be reported to Amgen via the Adverse Event Summary CRF. TVEs, and adverse events associated with RBC transfusions administered during the treatment period, that occur through the EOTP or 30 days after the last dose of IP, whichever occurs later, also will be documented in the CRF. VTEs are captured on a specific CRF page.

The investigator must assign the following adverse event attributes:

- Adverse event diagnosis or syndrome(s), if known (if not known, signs or symptoms)
- Event description (with detail appropriate to the event)
- Dates of onset and resolution
- Severity
- Assessment of relatedness to IP
- · Assessment of relatedness to transfusion
- Assessment of relatedness to chemotherapy
- Action taken

The adverse event severity grading scale used will be the CTCAE. The severity grading scale used in this study is described in Appendix B.

The investigator must assess whether the adverse event is possibly related to the IP. This relationship is indicated by a "yes" or "no" response to the question: "Is there a reasonable possibility that the event may have been caused by the IP?"

The investigator must assess whether the adverse event is possibly related to transfusion. This relationship is indicated by a "yes" or "no" response to the question: "Is there a reasonable possibility that the event may have been caused by RBC transfusion?"

The investigator must assess whether the adverse event is possibly related to chemotherapy. This relationship is indicated by a "yes" or "no" response to the question: "Is there a reasonable possibility that the event may have been caused by chemotherapy?"

Medically significant adverse events considered related to the IP by the investigator will be followed until resolved or considered stable.

The investigator's clinical judgment will be used to determine whether a subject should be removed from treatment or from the study due to an adverse event. A subject may also voluntarily withdraw from treatment due to an adverse event. If the subject is withdrawn, the subject should be strongly encouraged to undergo at a minimum an end-of-treatment assessment. The subject should be followed until symptoms cease or the condition becomes stable.

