9.2.2 Reporting Procedures for Serious Adverse Events

The Investigator is responsible for ensuring that all serious adverse events observed by the Investigator or reported by the subject that occur after signing of informed consent through 30 days after last dose of IP as recorded in the subject's medical record and are submitted to Amgen. Serious TVEs, and SAEs associated with RBC transfusions administered during the treatment period, that occur through the EOTP or 30 days after the last dose of IP, whichever occurs later, also will be reported to Amgen. During long-term follow-up period, SAEs will not be reported to Amgen, except for SAEs occurring after 30 days post last dose of IP AND thought to be possibly related to IP. These events are to be submitted to Amgen.

The serious adverse event must be submitted to Amgen within 24 hours following the Investigator's knowledge of the event via the applicable CRF. If the electronic

data capture (EDC) system is unavailable to the site staff to report the Serious Adverse Event, the information is to be reported to Amgen via a Serious Adverse Event (SAE) Contingency Reporting Form within 24 hours of the Investigator's knowledge of the event. See Appendix C for a sample of the Serious Adverse Event Contingency Reporting Form. If the first notification of a Serious Adverse Event is reported to Amgen via the Serious Adverse Event Contingency Reporting Form, the data must be entered into the EDC system when the system is again available.

New information relating to a previously reported serious adverse event must be submitted to Amgen. All new information for serious adverse events must be sent to Amgen within 24 hours following knowledge of the new information. The Investigator may be asked to provide additional follow-up information, which may include a discharge summary or extracts from the medical record; autopsy reports should be provided for deaths, if available. Information provided about the serious adverse event must be consistent with that recorded on the applicable CRF (eg, Adverse Event Summary CRF). If a subject is permanently withdrawn from the study because of a serious adverse event, this information must be submitted to Amgen.

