Appendix A. Schedule of Assessments

- a. The screening period, which starts when the subject signs and dates the ICF and ends when the subject is randomized or screen failed, must not exceed 21 days. The local laboratory hemoglobin sample to confirm the eligibility hemoglobin value ≤ 11.0 g/dL must be obtained within 7 days prior to randomization. If the pre-chemotherapy baseline scan was performed more than 28 days prior to randomization, an additional scan must be performed and reviewed by the investigator to confirm that the patient has not progressed before randomization.
- b. Vital signs include temperature and resting BP (systolic and diastolic). Weight, presence of new / replaced central or mid-line venous catheters, and radiotherapy information will be collected during screening and during the treatment period. Anti-cancer therapy and anti-cancer surgery information will be collected during the treatment period.
- c. All SAEs that occur after the subject signed the ICF through 30 days post last dose of IP will be collected. All AEs will be collected after randomization until 30 days post last dose of IP. Signs and symptoms of clinically relevant TVEs will be assessed at each visit during the treatment period. If present, appropriate labs, diagnostic, and imaging will be performed. All TVEs, and adverse events associated with RBC transfusions occurring during the treatment period, will be documented in the CRF through the EOTP or until 30 days after the last dose of IP, whichever occurs later.
- d. IP will be administered SC Q3W during the treatment period. IP will be discontinued within 3 weeks after the last dose of chemotherapy, or upon the determination of disease progression, whichever occurs first. Subjects who discontinued IP but have not had disease progression will continue Q3W visits and Q9W imaging studies until progression has been determined. Subjects who are unable to continue Q3W visits and Q9W imaging studies until disease progression should complete EOTP procedures at their next Q3W visit and will be asked to enter the LTFU period.
- e. Central lab clinical chemistries includes creatinine, bilirubin, ALT, AST. CRP will be performed at Day 1 only.
- f. Central lab CBC includes WBC with differential, hemoglobin, hematocrit, platelet count.

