Unspecified/mixed thromboembolic events include thromboembolic events where the vessel type is either unspecified or a mix of arterial and venous. These events will be coded using MedDRA version **20.0** (or higher) and identified using the sub-SMQ 20000083 ("embolic and thrombotic events, vessel type unspecified and mixed arterial and venous") or more appropriate query available at the time of analysis.

Time to Progression (TTP)

Time from randomization to date of radiographic disease progression. Subjects without progression will be censored on the date of their last disease assessment. Disease progression will be based on the investigator's assessment of scans using the version of RECIST specified in the protocol at the time of subject enrollment.

Treatment Group

Subjects were randomized to 1 of 2 treatment groups: darbepoetin alfa (500 μ g) Q3W or placebo Q3W in a 2:1 allocation.

Treatment-emergent Adverse Event

A treatment-emergent adverse event is an adverse reported via the adverse event summary eCRF with an onset date between study day 1 and 30 days after the last dose of IP, inclusive, with one exception: VTEs and adverse events associated with RBC transfusions can have an onset date of 30 days after the last dose of IP or the EOTP visit, whichever is later.

6. Analysis Sets

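### SAP Section 5 counts venous events to the end-of-treatment visit but arterial and unspecified/mixed events only to 30 days after last dose, and Section 9.6.4 gives a second, open-ended definition

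*SAP*

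**What the plan says.** **SAP Section 5 (Treatment-emergent Adverse Event).** Onset must fall between study day 1 and 30 days after the last IP dose. The single exception reads: "VTEs and adverse events associated with RBC transfusions can have an onset date of 30 days after the last dose of IP". For both of these event types, the EOTP visit replaces that limit when it falls later. Section 5 itself defines TVEs as three groups: arterial (ATE), venous (VTE) and unspecified/mixed. Only the venous group gets the longer window.

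**SAP Section 9.6.4.** Treatment-emergence is defined a second time, as onset after the first dose has been given. There is no end date, no exception and no reference to Section 5. The same section makes TVEs as a group an event of special interest and has all three sub-categories summarized so that the TVE total is fully broken down. It adds that ATEs by themselves are not of special interest.

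**SAP Section 2.1** lists TVE incidence among the other endpoints.

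**Protocol.** The extended collection window is set for TVEs, not for VTEs, in five places. In each, the 30 days run from the last dose and the later of the two dates applies:

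- Section 7.1.8, which names stroke, TIA and acute coronary syndromes among the TVEs: "TVEs will be documented in the CRF through the EOTP or 30 days after the last dose of IP, whichever occurs later".
- Section 7.1.10, for reporting to the sponsor: "All TVEs, and adverse events associated with RBC transfusions administered during the treatment period, will be reported through the EOTP or 30 days".
- Section 9.1.2, for the CRF: "TVEs, and adverse events associated with RBC transfusions administered during the treatment period, that occur through the EOTP or 30 days".
- Section 9.2.2, for serious events: "Serious TVEs, and SAEs associated with RBC transfusions administered during the treatment period, that occur through the EOTP or 30 days".
- Appendix A, footnote c: "All TVEs, and adverse events associated with RBC transfusions occurring during the treatment period, will be documented in the CRF through the EOTP".

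The glossary explains why the two end points can lie far apart: "Note that EOTP is based on disease progression, not IP dosing".

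**The concern.** Two things look wrong. First, the Section 5 exception has the same structure as the protocol's collection rule (a thrombotic event class plus transfusion-associated events, to the later of the same two dates), but it names VTEs where the protocol names TVEs. Late arterial and unspecified/mixed events are therefore on the CRF yet fall outside the treatment-emergent tables, unless they were recorded as transfusion-associated. Second, Section 9.6.4 would count those same events, so two programmers following the SAP faithfully could produce different TVE tables.

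At stake is the readability of a listed safety endpoint. Under Section 5 the TVE breakdown would set VTEs counted to EOTP beside ATEs and unspecified/mixed events counted only to last dose + 30 days, and add them up. The Section 5 events-of-interest list also names ischaemic heart disease including MI, and cerebrovascular disorders. These overlap the SAP's own ATE definition, so arterial events are not a side issue in this programme.

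**Working it through.** **1. The rules side by side**

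| Event type | Protocol collection ends | SAP Section 5 ends | SAP 9.6.4 ends |
|---|---|---|---|
| VTE | later of EOTP, last dose + 30 d | later of EOTP, last dose + 30 d | no end stated |
| ATE | later of EOTP, last dose + 30 d | last dose + 30 d | no end stated |
| Unspecified/mixed | later of EOTP, last dose + 30 d | last dose + 30 d | no end stated |
| Transfusion-associated AE | later of EOTP, last dose + 30 d | later of EOTP, last dose + 30 d | no end stated |
| Other AE | last dose + 30 d | last dose + 30 d | no end stated |

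For ordinary AEs the SAP definitions nearly agree, because collection itself stops at last dose + 30 days. They diverge for ATEs and unspecified/mixed events between that date and EOTP, and for late SAEs thought related to IP, which protocol Section 9.2.2 still requires to be submitted. The start points differ slightly too: Section 5 uses the calendar day of first dose, 9.6.4 uses the time after that dose is given.

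**2. Length of the gap for one subject**

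Inputs: the protocol's visit and scan weeks (Appendix A), with EOTP at the next three-weekly visit after progression. The dosing and progression dates are chosen for illustration.

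- Day = (week − 1) × 7 + 1. Week 10 = day 64, week 16 = day 106, week 19 = day 127, week 22 = day 148, week 28 = day 190, week 31 = day 211.
- Gap = max(0, EOTP day − (last IP day + 30)).

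| Last IP | Progression | EOTP | Last IP + 30 | Gap |
|---|---|---|---|---|
| day 127 | day 127 | day 148 | day 157 | 0 days |
| day 106 | day 127 | day 148 | day 136 | 148 − 136 = 12 days |
| day 64 | day 127 | day 148 | day 94 | 148 − 94 = 54 days |
| day 64 | day 190 | day 211 | day 94 | 211 − 94 = 117 days |

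In the last row, a stroke on day 150 is collected, excluded by Section 5 and included by 9.6.4. A pulmonary embolism on the same day is counted under both.

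**3. How many subjects could have a gap (assumptions, not trial figures)**

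The documents give neither a PFS median nor the distribution of IP stop times. Assume:

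- exponential PFS with a median of 4.5 or 6 months;
- a planned IP stop time U, uniform over the weeks shown, with last IP the earlier of U and progression;
- EOTP at progression + V, with V uniform on 0 to 21 days.

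A gap then needs progression later than U + 30 − V, so with hazard λ per day

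share = E[exp(−λU)] × exp(−30λ) × E[exp(λV)].

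For a 4.5-month median and stop at weeks 6 to 12 (days 42 to 84): λ = ln 2 / (4.5 × 365.25/12) = 0.00506, and the three factors are 0.728, 0.859 and 1.055. Their product is 0.66. A simulation of 1,000,000 subjects per scenario gives the same values:

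| IP stop (weeks) | Median 4.5 months | Median 6 months |
|---|---|---|
| 6–12 | 66% | 73% |
| 9–18 | 56% | 65% |
| 9–28 | 48% | 57% |
| 18–28 | 40% | 51% |
| 18–52 | 28% | 38% |

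The last row represents IP continued through maintenance, which protocol Section 6.2.2 allows: "if optional myelosuppressive maintenance therapy is initiated, then the subject may receive IP as scheduled" while myelosuppressive chemotherapy continues. If 20% of subjects complete EOTP early, within 21 days of last IP, each share is multiplied by 0.8 and the extremes become 22% and 59%. Letting 20% of PFS events be deaths with no later EOTP visit moves the shares by less than 1 percentage point. These are shares of subjects with a gap, not of events lost.

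**The case against.** The case for leaving the text alone has real points. Section 5 is the Definitions section and gives a full window, so the 9.6.4 sentence may be shorthand. A focus on VTEs also looks partly deliberate: they have their own tables, a primary and sensitivity rule based on imaging, first-priority status in Section 12, and the only thromboembolic query in the events-of-interest list. ATEs alone are said not to be of special interest. Tabulating less than is collected is not an error in itself. Nor can silence in SAP Section 10 show a departure from the protocol, because the protocol's analysis text for other safety endpoints is redacted.

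The last two points stand, and no departure from a protocol analysis is claimed. The rest does not remove the problem. A focus on VTEs does not explain why unspecified/mixed events are left out, or why a TVE total should add counts from two risk periods. The remark about ATEs says they are not a stand-alone category; it sets no window and does not take them out of the total. If 9.6.4 is shorthand, the SAP should say so.

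Two limits on the remedy also stand. The ischaemic heart disease and cerebrovascular categories include events that are not TVEs and are mostly not collected past last dose + 30 days, so extending the window for TVEs would leave those categories with mixed windows. And IP-related SAEs with onset after EOTP, which 9.6.4 would count, would still fall outside a window ending at EOTP.

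**Conclusion.** The concern holds. SAP Sections 5 and 9.6.4 contradict each other, and Section 5 as written leaves out collected late arterial and unspecified/mixed TVEs while counting VTEs from the same days. This rests on the text alone and is firm.

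Size: a gap of 0 to 117 days per subject in the cases worked. The share of subjects with any gap is 28% to 73%, or 22% to 59% with early EOTP in 20%, and depends entirely on assumed PFS and stop times. The number of events affected cannot be derived from the documents.

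The consequence is confined to descriptive special-interest safety tables. Overall survival, PFS and the transfusion endpoint do not change, fatal late arterial events still count in overall survival, and no bias between arms is claimed. It should be corrected, but it does not threaten the main conclusions.

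**What to change.** 1. In SAP Section 5, widen the exception from VTEs to all TVEs (venous, arterial and unspecified/mixed), keeping transfusion-associated AEs, with onset up to the later of 30 days after the last IP dose or the EOTP visit.
2. In Section 9.6.4, replace the sentence defining treatment-emergence with a reference to Section 5, so that one start and one end apply.
3. If the VTE-only window is intended, say so and give the reason, and show the three TVE components and their total over one common window.
4. Footnote the ischaemic heart disease and cerebrovascular tables to say that only their TVE, transfusion-associated and IP-related serious members can be collected past last dose + 30 days. State how IP-related SAEs with onset after EOTP will be shown, for example in a listing.

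Items 1 and 2 cost two SAP sentences and one programming rule; item 4 adds a footnote and at most a listing. No new data are needed, because the protocol already puts these TVEs on the CRF through EOTP.

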6.1 Primary Analysis Set

The primary analysis set will include all randomized and consented subjects with non-small cell lung cancer who receive at least one dose of investigational product. Subjects will be analyzed according to their randomized treatment group. The analysis of overall survival, progression-free survival, time to progression, response-related endpoints, serious AEs, events of interest, VTE and all efficacy endpoints (except for the endpoint of transfusion or hemoglobin ≤ 8.0 g/dL from day 29 to EOETP) will be performed using the primary analysis set.

